**17.4.2.1.2.2. Tumor Necrosis Factor Alpha (TNF- $\alpha$ ) Inhibitors**

adalimumab
afelimomab
certolizumab pegol
etanercept
golimumab
infliximab
opinercept

**17.4.2.1.2.3. Interleukin Inhibitors**

anakinra
basiliximab
bimekizumab
briakinumab
brodalumab
canakinumab
daclizumab
guselkumab
ixekizumab
netakimab
olokizumab
rilonacept
risankizumab
sarilumab
satralizumab
secukinumab
siltuximab
sirukumab
spesolimab
tildrakizumab
tocilizumab
ustekinumab

**17.4.2.1.2.4. Calcineurin Inhibitors**

cyclosporine
tacrolimus
voclosporin

090177e1a5be86fe\Approved\Approved On: 19-Mar-2026 15:57 (GMT)

#### **17.4.2.1.2.5. Other Immunosuppressants**

azathioprine
darvadstrocel
dimethyl fumarate
diroximel fumarate
lenalidomide
methotrexate
pirfenidone
pomalidomide
thalidomide

#### **17.4.2.1.3. Chemotherapeutic Agents**

##### **17.4.2.1.3.1. Alkylating Agents**

chlorambucil  
cisplatin  
cyclophosphamide

##### **17.4.2.1.3.2. Antimetabolite Agents**

5-fluorouracil  
6-mercaptopurine  
cytarabine  
methotrexate

##### **17.4.2.1.3.3. Antitumor Antibiotics**

bleomycin  
doxorubicin  
mitomycin C

##### **17.4.2.1.3.4. Mitotic Inhibitors**

paclitaxel  
plant alkaloids (vinblastine, vincristine)

##### **17.4.2.1.3.5. Topoisomerase Inhibitors**

etoposide  
irinotecan  
opotecan

#### **17.4.2.1.4. Myelosuppressive Agents**

hydroxyurea

090177e1a5be86fe\Approved\Approved On: 19-Mar-2026 15:57 (GMT)

#### 17.4.2.1.5. ICD-10-CM, CPT and HCPCS Codes

In addition to NDC codes for the above, the following ICD-10, CPT and HCPCS codes will be used:

##### **ICD-10-CM:**

T45.1***	Poisoning by, adverse effect of and underdosing of antineoplastic and immunosuppressive drugs
Z79.6	Long term (current) use of immunomodulators and immunosuppressants
Z79.60	Long term (current) use of unspecified immunomodulators and immunosuppressants
Z79.61	Long term (current) use of immunomodulator (apremilast, immunomodulatory imide drug, lenalidomide, pomalidomide)
Z79.62	Long term (current) use of immunosuppressant
Z79.620	Long term (current) use of immunosuppressive biologic (adalimumab, etanercept, infliximab, monoclonal antibodies)
Z79.621	Long term (current) use of calcineurin inhibitor (cyclosporine, tacrolimus)
Z79.622	Long term (current) use of Janus kinase inhibitor (tofacitinib)
Z79.623	Long term (current) use of mammalian target of rapamycin (mTOR) inhibitor (sirolimus)
Z79.624	Long term (current) use of inhibitors of nucleotide synthesis (azathioprine, mycophenolate, purine synthesis (IMDH) inhibitors)
Z79.63	Long term (current) use of chemotherapeutic agent
Z79.630	Long term (current) use of alkylating agent (chlorambucil, cisplatin, cyclophosphamide)
Z79.631	Long term (current) use of antimetabolite agent (5-fluorouracil, 6-mercaptopurine, cytarabine, methotrexate)

---

 CPT copyright 2024 American Medical Association. All rights reserved.

Z79.632	Long term (current) use of antitumor antibiotic (bleomycin, doxorubicin, mitomycin C)
Z79.633	Long term (current) use of mitotic inhibitor (paclitaxel, plant alkaloids, vinblastine, vincristine)
Z79.634	Long term (current) use of topoisomerase inhibitor (etoposide, irinotecan, topotecan)
Z79.64	Long term (current) use of myelosuppressive agent (hydroxyurea)
Z79.69	Long term (current) use of other immunomodulators and immunosuppressants

**ICD-10-PCS:**

3E03302	Introduction of High-dose Interleukin-2 into Peripheral Vein, Percutaneous Approach
3E03303	Introduction of Low-dose Interleukin-2 into Peripheral Vein, Percutaneous Approach
3E04002	Introduction of High-dose Interleukin-2 into Central Vein, Open Approach
3E04003	Introduction of Low-dose Interleukin-2 into Central Vein, Open Approach
3E04302	Introduction of High-dose Interleukin-2 into Central Vein, Percutaneous Approach
3E04303	Introduction of Low-dose Interleukin-2 into Central Vein, Percutaneous Approach
3E05002	Introduction of High-dose Interleukin-2 into Peripheral Artery, Open Approach
3E05302	Introduction of High-dose Interleukin-2 into Peripheral Artery, Percutaneous Approach
3E050WK	Introduction of Immunostimulator into Peripheral Artery, Open
3E050WL	Introduction of Immunosuppressive into Peripheral Artery, Open

090177e1a5be86fe\Approved\Approved On: 19-Mar-2026 15:57 (GMT)

3E053WL	Introduction of Immunosuppressive into Peripheral Artery, Percutaneous
3E053WL	Introduction of Immunosuppressive into Peripheral Artery, Percutaneous
3E060WK	Introduction of Immunostimulator into Central Artery, Open
3E060WL	Introduction of Immunosuppressive into Central Artery, Open
3E063WK	Introduction of Immunostimulator into Central Artery, Percutaneous
3E063WL	Introduction of Immunosuppressive into Central Artery, Percutaneous
XW01397	Introduction of Satralizumab-mwge into Subcutaneous Tissue, Percutaneous Approach, New Technology Group 7
XW033C6	Introduction of Eculizumab into Peripheral Vein, Percutaneous Approach, New Technology Group 6
XW033H5	Introduction of Tocilizumab into Peripheral Vein, Percutaneous Approach, New Technology Group 5
XW033L6	Introduction of CD24Fc Immunomodulator into Peripheral Vein, Percutaneous Approach, New Technology Group 6
XW033L7	Introduction of Lifileucel Immunotherapy into Peripheral Vein, Percutaneous Approach, New Technology Group 7
XW033M7	Introduction of Brexucabtagene Autoleucel Immunotherapy into Peripheral Vein, Percutaneous Approach, New Technology Group 7
XW03308	Introduction of Spesolimab Monoclonal Antibody into Peripheral Vein, Percutaneous Approach, New Technology Group 8
XW03398	Introduction of Inebilizumab-cdon into Peripheral Vein, Percutaneous Approach, New Technology Group 8
XW04308	Introduction of Spesolimab Monoclonal Antibody into Central Vein, Percutaneous Approach, New Technology Group 8
XW04398	Introduction of Inebilizumab-cdon into Central Vein, Percutaneous Approach, New Technology Group 8

XW043G5	Introduction of Sarilumab into Central Vein, Percutaneous Approach, New Technology Group 5
XW043H5	Introduction of Tocilizumab into Central Vein, Percutaneous Approach, New Technology Group 5
XW043L6	Introduction of CD24Fc Immunomodulator into Central Vein, Percutaneous Approach, New Technology Group 6
XW0DXM6	Introduction of Baricitinib into Mouth and Pharynx, External Approach, New Technology Group 6
XW0G7M6	Introduction of Baricitinib into Upper GI, Via Natural or Artificial Opening, New Technology Group 6
XW0H7M6	Introduction of Baricitinib into Lower GI, Via Natural or Artificial Opening, New Technology Group 6

**CPT**

80145	Adalimumab
80158	Cyclosporine
80169 	Everolimus
80180	Mycophenolate (mycophenolic acid)
80193	Leflunomide
80195	Sirolimus
80197	Tacrolimus
80180	Mycophenolate (mycophenolic acid)
80204	Methotrexate
80230	Infliximab
80280	Vedolizumab

---

 CPT copyright 2024 American Medical Association. All rights reserved.

 CPT copyright 2024 American Medical Association. All rights reserved.

- 90585 Bacillus Calmette-Guerin vaccine (BCG) for tuberculosis, live, for percutaneous use
- 90586 Bacillus Calmette-Guerin vaccine (BCG) for bladder cancer, live, for intravesical use

**HCPCS**

- J0129 Injection, abatacept, 10 mg (code may be used for Medicare when drug administered under the direct supervision of a physician, not for use when drug is self-administered)
- J0135 Injection, adalimumab, 20 mg
- S0176 Hydroxyurea, oral, 500 mg
- J0215 Injection, alefacept, 0.5 mg
- J0202 Injection, alemtuzumab, 1 mg
- J0480 Injection, basiliximab, 20 mg
- J0485 Injection, belatacept, 1 mg
- J0490 Injection, belimumab, 10 mg
- J0491 Injection, anifrolumab-fnia, 1 mg
- J0638 Injection, canakinumab, 1 mg
- J0717 Injection, certolizumab pegol, 1 mg (code may be used for Medicare when drug administered under the direct supervision of a physician, not for use when drug is self-administered)
- J1300 Injection, eculizumab, 10 mg
- J1302 Injection, sutimlimab-jome, 10 mg
- J1303 Injection, ravulizumab-cwvz, 10 mg
- J1438 Injection, etanercept, 25 mg (code may be used for Medicare when drug administered under the direct supervision of a physician, not for use when drug is self-administered)
- J1442 Injection, filgrastim (G-CSF), excludes biosimilars, 1 mcg
- J1447 Injection, tbo-filgrastim, 1 mcg

J1449	Injection, eflapegrastim-xnst, 0.1 mg
J1595	Injection, glatiramer acetate, 20 mg
J1602	Injection, golimumab, 1 mg, for intravenous use
J1628	Injection, guselkumab, 1 mg
J1745	Injection, infliximab, excludes biosimilar, 10 mg
J1747	Injection, spesolimab-sbzo, 1 mg
J1823	Injection, inebilizumab-cdon, 1 mg
J1826	Injection, interferon beta-1a, 30 mcg
J1830	Injection interferon beta-1b, 0.25 mg (code may be used for Medicare when drug administered under the direct supervision of a physician, not for use when drug is self-administered)
J2323	Injection, natalizumab, 1 mg
J2327	Injection, risankizumab-rzaa, intravenous, 1 mg
J2329	Injection, ublituximab-xiyy, 1mg
J2350	Injection, ocrelizumab, 1 mg
J2355	Injection, oprelvekin, 5 mg
J2504	Injection, pegademase bovine, 25 IU
J2506	Injection, pegfilgrastim, excludes biosimilar, 0.5 mg
J2562	Injection, plerixafor, 1 mg
J2781	Injection, pegcetacoplan, intravitreal, 1 mg
J2793	Injection, rilonacept, 1 mg
J2820	Injection, sargramostim (GM-CSF), 50 mcg
J2860	Injection, siltuximab, 10 mg
J3241	Injection, teprotumumab-trbw, 10 mg

090177e1a5be86fe\Approved\Approved On: 19-Mar-2026 15:57 (GMT)

J3245	Injection, tildrakizumab, 1 mg J3380 Injection, vedolizumab, 1 mg
J3262	Injection, tocilizumab, 1 mg
J3357	Ustekinumab, for subcutaneous injection, 1 mg
J3358	Ustekinumab, for intravenous injection, 1 mg
J7500-J7599:	Immunosuppressive drugs
J8560	Etoposide, oral, 50 mg
J8610	Methotrexate, oral, 2.5 mg
J9000	Injection, doxorubicin HCl, 10 mg
J9015	Injection, aldesleukin, per single use vial
J9030	BCG live intravesical instillation, 1 mg
J9037	Injection, belantamab mafodotin-blmf, 0.5 mg
J9040	Injection, bleomycin sulfate, 15 units
J9060	Injection, cisplatin, powder or solution, 10 mg
J9065	Injection, cladribine, per 1 mg J9047 Injection, carfilzomib, 1 mg
J9070	Cyclophosphamide, 100 mg
J9071	Injection, cyclophosphamide, (AuroMedics), 5 mg
J9098	Injection, cytarabine liposome, 10 mg
J9100	Injection, cytarabine, 100 mg
J9145	Injection, daratumumab, 10 mg
J9144	Injection, daratumumab, 10 mg and hyaluronidase-fihj
J9153	Injection, liposomal, 1 mg daunorubicin and 2.27 mg cytarabine
J9176	Injection, elotuzumab, 1 mg
J9181	Injection, etoposide, 10 mg

J9190	Injection, fluorouracil, 500 mg
J9205	Injection, irinotecan liposome, 1 mg
J9206	Injection, irinotecan, 20 mg
J9210	Injection, emapalumab-lzsg, 1 mg
J9212	Injection, interferon alfacon-1, recombinant, 1 mcg
J9213	Injection, interferon, alfa-2a, recombinant, 3 million units
J9214	Injection, interferon, alfa-2b, recombinant, 1 million units
J9215	Injection, interferon, alfa-N3, (human leukocyte derived), 250,000 IU
J9216	Injection, interferon, gamma 1-b, 3 million units
J9247	Injection, melphalan flufenamide, 1 mg
J9250	Methotrexate sodium, 5 mg
J9259	Injection, paclitaxel protein-bound particles (American Regent) not therapeutically equivalent to J9264, 1 mg
J9260	Methotrexate sodium, 50 mg
J9264	Injection, paclitaxel protein-bound particles, 1 mg
J9267	Injection, paclitaxel, 1 mg
J9302	Injection, ofatumumab, 10 mg
J9331	Injection, sirolimus protein-bound particles, 1 mg
J9332	Injection, efgartigimod alfa-fcab, 2 mg
J9360	Injection, vinblastine sulfate, 1 mg
J9370	Vincristine sulfate, 1 mg
J9371	Injection, vincristine sulfate liposome, 1 mg
J9380	Injection, teclistamab-cqyv, 0.5 mg

090177e1a5be86fe\Approved\Approved On: 19-Mar-2026 15:57 (GMT)

M0249	Intravenous infusion, tocilizumab, for hospitalized adults and pediatric patients (2 years of age and older) with COVID-19 who are receiving systemic corticosteroids and require supplemental oxygen, non-invasive or invasive mechanical ventilation
M0250	Intravenous infusion, tocilizumab, for hospitalized adults and pediatric patients (2 years of age and older) with COVID-19 who are receiving systemic corticosteroids and require supplemental oxygen, non-invasive or invasive mechanical ventilation
Q0249	Injection, tocilizumab, for hospitalized adults and pediatric patients (2 years of age and older) with COVID-19 who are receiving systemic corticosteroids and require supplemental oxygen, non-invasive or invasive mechanical ventilation, or extracorporeal
Q0510	Pharmacy supply fee for initial immunosuppressive drug(s), first month following transplant
Q2043	Sipuleucel-T, minimum of 50 million autologous CD54+ cells activated with PAP-GM-CSF, including leukapheresis and all other preparatory procedures, per infusion
Q2049	Injection, doxorubicin HCl, liposomal, imported Lipodox, 10 mg
Q2050	Injection, doxorubicin HCl, liposomal, not otherwise specified, 10 mg
Q2056	Ciltacabtagene autoleucel, up to 100 million autologous B-cell maturation antigen (BCMA) directed CAR-positive T cells, including leukapheresis and dose preparation procedures, per therapeutic dose
Q2055	Idecabtagene vicleucel, up to 460 million autologous B-cell maturation antigen (BCMA) directed CAR-positive T cells, including leukapheresis and dose preparation procedures, per therapeutic dose
Q3027	Injection, interferon beta-1a, 1 mcg for intramuscular use
Q3028	Injection, interferon beta-1a, 1 mcg for subcutaneous use
Q5101	Injection, filgrastim-sndz, biosimilar, (Zarxio), 1 mcg

Q5103	Injection, infliximab-dyyb, biosimilar, (Inflectra), 10 mg
Q5104	Injection, infliximab-abda, biosimilar, (Renflexis), 10 mg
Q5108	Injection, pegfilgrastim-jmdb (Fulphila), biosimilar, 0.5 mg
Q5109	Injection, infliximab-qbtx, biosimilar, (Ixifi), 10 mg Q5121 Injection, infliximab-axxq, biosimilar, (AVSOLA), 10 mg
Q5110	Injection, filgrastim-aafi, biosimilar, (Nivestym), 1 mcg
Q5111	Injection, pegfilgrastim-cbqv (Udenyca), biosimilar, 0.5 mg
Q5120	Injection, pegfilgrastim-bmez (ZIEXTENZO), biosimilar, 0.5 mg
Q5122	Injection, pegfilgrastim-apgf (Nyvepria), biosimilar, 0.5 mg
Q5125	Injection, filgrastim-ayow, biosimilar, (Releuko), 1 mcg
Q5127	Injection, pegfilgrastim-fpgk (Stimufend), biosimilar, 0.5 mg
Q5130	Injection, pegfilgrastim-pbbk (Fylnetra), biosimilar, 0.5 mg
Q5131	Injection, adalimumab-aacf (Idacio), biosimilar, 20 mg
S0145	Injection, PEGylated interferon alfa-2A, 180 mcg per ml
S0148	Injection, PEGylated interferon alfa-2B, 10 mcg
S0172	Chlorambucil, oral, 2 mg

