#### 9.1.1. SCRI

Phase 1 will monitor the incidence rate of pre-specified safety events of interest in a general population of individuals who receive the COMIRNATY 2023-2024 Formula using an SCRI study design that tracks post-vaccination risk intervals and control (reference) periods for each vaccinated individual. Monitoring will be conducted during a pre-specified risk period immediately following vaccination, and the observed rate of events during this risk period will be compared to that of a control period temporally removed from the vaccination event. As depicted in [Figure 1](#), only individuals who receive the COMIRNATY 2023-2024 Formula will be included in the SCRI study ([Baker et al., 2015](#)). Within each individual, outcomes occurring during the risk interval will be compared with those occurring during the control period, in order to determine whether these outcomes occur more frequently immediately after vaccination as compared with a reference period. A washout period may be inserted between the risk interval and the control period to ensure that events relating to the vaccine are not incorrectly attributed to the control period. To ensure that observed outcomes are truly incident, a period free from the outcome of interest (clean period) may be required prior to vaccination.

090177e1a5be86fe\Approved\Approved On: 19-Mar-2026 15:57 (GMT)

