#### **9.2.2.2. Exclusion Criteria**

Patients meeting any of the following criteria will not be included in Phase 2 of the study:

1. Are of unknown sex.
2. Have a missing month and year of birth.
3. Have received a COVID-19 vaccine in the 270 days prior to cohort entry date (as defined in Section 9.2.3).
4. Have received both the COMIRNATY 2023-2024 Formula and a COVID-19 vaccine other than the COMIRNATY 2023-2024 Formula on the cohort entry date (defined in Section 9.2.3).

In both phases of the study, when creating the analytic population for each specific safety outcome of interest, individuals will be excluded if they experienced that safety outcome during the portion of the baseline period designated as the clean period ([Section 9.2.4](#)).

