## 9.9. Limitations of the Research Methods

The proposed project is based on analysis of automated medical and prescription claims, including pre-adjudicated (interim reporting) and fully adjudicated claims (final reporting).

For the interim report, the SCRI analysis will be based on automated and prospectively collected pre-adjudicated medical and adjudicated prescription claims. A strength of pre-adjudicated medical claims is the shorter lag time between the receipt of care and the appearance of the claim, while the accompanying limitation is that these pre-adjudicated claims may be subject to revision during the adjudication process. A limitation of the SCRI design may be its limited ability to assess chronic outcomes such as MS. Thus, the cohort analysis will be used as the primary analysis for chronic outcomes.

While adjudicated claims data are extremely valuable for the efficient and effective examination of healthcare outcomes, treatment patterns, healthcare resource utilization, and costs, all claims databases have certain inherent limitations because the claims are collected for the purpose of payment, not research. The presence of a diagnosis code on a medical

claim is not confirmation of disease, as the diagnosis code may be incorrectly coded or included as rule-out criteria rather than actual disease.

Another limitation of claims data relates to potential misclassification of exposure covariates. For instance, vaccines that are administered as part of a government program or an office-based or school-based vaccination clinic may not be captured in our database if insurance information was not provided during the vaccine encounter. This potential exposure misclassification is minimized in the self-controlled design in Phase 1; misclassification of exposure in Phase 2 would be expected to bias the results towards the null (CDC, 2023e). Furthermore, the presence of a claim for a filled prescription does not indicate that the medication was consumed or that it was taken as prescribed. Medications paid for out-of-pocket, as well as those not dispensed through a pharmacy, will not be observed in the claims data. Similarly, we may not have complete history of comorbidity or treatment for individuals due to switching in health plan insurer.

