### 17.3. Appendix III – Safety Outcomes of Interest

All codes are ICD-10 diagnosis codes; all outcomes will be defined based on the presence of a single code unless otherwise specified. In order to qualify as an outcome, the outcome-specific codes must be identified during emergency department visits, inpatient hospitalizations, or outpatient visits, as detailed in [Table 2](#). Outpatient visits are defined through physician evaluation and management codes ([Section 17.2.3](#)).

\* Outcome codes marked with an asterisk are based on COVID-19 vaccine studies conducted as part of the FDA’s CBER BEST system.

- Acute disseminated encephalomyelitis (ADEM)\*
  - G04.00 – Acute disseminated encephalitis and encephalomyelitis, unspecified
- Anaphylaxis\*
  - T80.52XA – Anaphylactic reaction due to vaccination, initial encounter
  - T78.2XXA – Anaphylactic shock, unspecified, initial encounter
- Bell's palsy\*
  - G51.0 – Bell’s palsy
  - G51.8 – Other disorders of facial nerve
  - G51.9 – Disorder of facial nerve, unspecified
- Cerebral venous sinus thrombosis (CVST)
  - I67.6 – Nonpyogenic thrombosis of intracranial venous system
  - I63.6 – Cerebral infarction due to cerebral venous thrombosis, nonpyogenic
- Convulsions/seizures (non-febrile)
  - G40.001 – Localization-related (focal) (partial) idiopathic epilepsy and epileptic syndromes with seizures of localized onset, not intractable, with status epilepticus
  - G40.009 – Localization-related (focal) (partial) idiopathic epilepsy and epileptic syndromes with seizures of localized onset, not intractable, without status epilepticus
  - G40.011 – Localization-related (focal) (partial) idiopathic epilepsy and epileptic syndromes with seizures of localized onset, intractable, with status epilepticus
  - G40.019 – Localization-related (focal) (partial) idiopathic epilepsy and epileptic syndromes with seizures of localized onset, intractable, without status epilepticus
  - G40.101 – Localization-related (focal) (partial) symptomatic epilepsy and epileptic syndromes with simple partial seizures, not intractable, with status epilepticus

090177e1a5be86fe\Approved\Approved On: 19-Mar-2026 15:57 (GMT)

- G40.109 – Localization-related (focal) (partial) symptomatic epilepsy and epileptic syndromes with simple partial seizures, not intractable, without status epilepticus

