      - M33.21 – Polymyositis with respiratory involvement
      - M33.22 – Polymyositis with myopathy

- M33.29 – Polymyositis with other organ involvement
- M33.9 – Dermatopolymyositis, unspecified
- M33.90 – Dermatopolymyositis, unspecified, organ involvement unspecified
- M33.91 – Dermatopolymyositis, unspecified with respiratory involvement
- M33.92 – Dermatopolymyositis, unspecified myopathy
- M33.93 – Dermatopolymyositis, unspecified without myopathy
- M33.99 – Dermatopolymyositis, unspecified with other organ involvement
- G72.41 – Other and unspecified myopathies
- G72.0 – Drug-induced myopathy
- G72.2 – Myopathy due to other toxic agents
- G72.41 – Inflammatory and immune myopathies, not elsewhere
- G72.49 – Other inflammatory and immune myopathies, not elsewhere classified
- G72.8 – Other specified myopathies
- G72.9 – Myopathy, unspecified
- G73.7 – Myopathy in diseases classified elsewhere
- M36.0 – Dermato(poly)myositis in neoplastic disease
- I42.7 – Cardiomyopathy due to drug and external agent
- I42.9 – Cardiomyopathy, unspecified
- I43 – Cardiomyopathy in diseases classified elsewhere
- I42 – Cardiomyopathy
- M79.1 – Myalgia
- M79.7 – Fibromyalgia
- I42.5 – Other restrictive cardiomyopathy
- I42.8 – Other cardiomyopathies
- Immune thrombocytopenia\*
  - D69.3 – Immune thrombocytopenic purpura
- Kawasaki disease\*
  - M30.3 – Mucocutaneous lymph node syndrome [Kawasaki]
- Multi inflammatory syndrome (in children and adults)\*
  - U07.1 – COVID-19 **and one of the following:**
  - M35.8 – Other specified systemic involvement of connective tissue

- M35.81 – Multisystem inflammatory syndrome
- M35.89 – Other specified systemic involvement of connective tissue
- Multiple sclerosis
  - G35 – Multiple sclerosis
- Myocardial infarction\*
  - I21.01 – ST elevation (STEMI) myocardial infarction involving left main coronary artery
  - I21.02 – ST elevation (STEMI) myocardial infarction involving left anterior descending coronary artery
  - I21.09 – ST elevation (STEMI) myocardial infarction involving other coronary artery of anterior wall
  - I21.11 – ST elevation (STEMI) myocardial infarction involving right coronary artery
  - I21.19 – ST elevation (STEMI) myocardial infarction involving other coronary artery of inferior wall
  - I21.21 – ST elevation (STEMI) myocardial infarction involving left circumflex coronary artery
  - I21.29 – ST elevation (STEMI) myocardial infarction involving other sites

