**17.4.2.1.1.2. Interferons**

albinterferon alfa-2b
cepeginterferon alfa-2b
interferon alfa natural
interferon alfa-2a
interferon alfa-2b
interferon alfacon-1
interferon alfa-n1
interferon beta natural
interferon beta-1a
interferon beta-1b
interferon gamma
peginterferon alfa-2a
peginterferon alfa-2a, combinations
peginterferon alfa-2b

090177e1a5be86fe\Approved\Approved On: 19-Mar-2026 15:57 (GMT)

peginterferon alfa-2b, combinations
peginterferon alfacon-2
peginterferon beta-1a
ropeginterferon alfa-2b

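### Existing multiple sclerosis can be counted as new, because the clean period screens only on the G35 outcome and ignores MS drug claims that the protocol already extracts

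*Protocol*

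**What the plan says.** **Outcome.** Section 17.3 defines MS as "G35 – Multiple sclerosis". Its general rule is that "all outcomes will be defined based on the presence of a single code unless otherwise specified", and nothing more is specified for MS. Table 2 gives MS a clean period of Days -365 to 0, a risk interval of Days 1 to 42, and inpatient (IP) or outpatient (OP) care as the setting.

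**Clean period.** Section 9.2.2.2 states, for both phases, that "individuals will be excluded if they experienced that safety outcome during the portion of the baseline period designated as the clean period". Criterion 5 of Section 9.2.1.1 says the same for the self-controlled (SCRI) phase. Section 9.1.1 gives the purpose: "To ensure that observed outcomes are truly incident".

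**Which analysis carries MS.** Section 9.9 names MS as a chronic outcome that the SCRI handles poorly and concludes that "the cohort analysis will be used as the primary analysis for chronic outcomes". Cohort follow-up runs up to one year (Section 9.2.5.2).

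**Drugs.** Section 17.4.2.1 lists "interferon beta-1a", interferon beta-1b, peginterferon beta-1a, glatiramer, ocrelizumab, ublituximab, fingolimod, siponimod, ponesimod, teriflunomide, and dimethyl and diroximel fumarate, and takes every NDC for them. The HCPCS list in 17.4.2.1.5 adds J1595 ("Injection, glatiramer acetate, 20 mg"), J1826, J1830, J2329, J2350, Q3027 and Q3028. Under Section 9.3.3 these agents form part of one binary covariate, systemic immunomodulators, which enters the propensity score model in Section 9.7.2.1.

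**Outpatient codes.** Section 17.3 says "Outpatient visits are defined through physician evaluation and management codes". The Table 2 footnote is broader and counts outpatient facility claims and professional claims.

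**The concern.** The clean period is meant to leave only new disease, but for MS it looks only for a diagnosis code that itself meets the outcome definition. Someone under continuous MS treatment can go through the baseline year without such a code, for example when two G35 visits fall more than 365 days apart. That person then stays at risk, and the next routine G35 visit within the follow-up year becomes a new case.

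The information that would identify such a person is already in the extract but is not used for this purpose. Section 7 calls the document a combined protocol and statistical analysis plan, so the exclusion rule stands as written here.

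What is at stake is the MS rate ratio in the design declared primary for chronic outcomes. Because people living with MS outnumber new diagnoses in a year (the ratio is assumed below), even a small leak could make up a visible share of the counted cases.

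**Working it through.** The protocol states no MS rate, sample size or share of prevalent cases, so there is no figure of its own to reproduce. The first step below rests on the text. The others illustrate size under stated assumptions.

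**1. Path through the rules.** Take a person with MS who fills an oral or self-injected MS drug all year.
- The pharmacy claim fields listed in Section 9.4.1 are NDC, drug name, dosage form, strength, fill date, days of supply, cost, and patient and prescriber codes. None is a diagnosis, so refills leave no G35. (Section 9.4.2 gives no field list for the research database; I assume it is the same.)
- With no qualifying G35 visit in Days -365 to 0, Section 9.2.2.2 does not exclude the person.
- The drug sets the immunomodulator covariate to yes. Matching may balance such people between groups but does not remove them.
- One later G35 visit meets the outcome definition.

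**2. Equal leak.** Let f be the share of counted comparator cases that are prevalent, with recoding of existing MS equally frequent in both groups and unaffected by the vaccine. Then RR observed = 1 + (RR true - 1)(1 - f). The true RR needed to read above the 3.0 threshold of Section 9.3.2 is 1 + 2/(1 - f).

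| f (assumed) | True RR 2 reads | True RR 3 reads | True RR needed to read above 3.0 |
|---|---|---|---|
| 0.1 | 1.90 | 2.80 | 3.22 |
| 0.3 | 1.70 | 2.40 | 3.86 |
| 0.5 | 1.50 | 2.00 | 5.00 |

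**3. Leak needed for such shares.** Let R be the ratio of MS prevalence to annual incidence (assumed 20 to 40), and u the share of prevalent patients who pass the clean period and are recoded within the year. Then f = Ru/(1 + Ru).
- u = 0.1%: f = 0.02 to 0.04
- u = 0.5%: f = 0.09 to 0.17
- u = 1%: f = 0.17 to 0.29
- u = 3%: f = 0.375 to 0.55

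Solving for u gives u = f/[R(1 - f)]. A share of 0.1 needs a leak of 0.28% (R = 40) to 0.56% (R = 20). A share of 0.5 needs 2.5% to 5%.

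**4. Unequal leak.** Day 0 lies inside the clean period. A comparator who enters on an office visit coded G35 is removed; a recipient vaccinated at a pharmacy has no such visit. Let Day 0 remove a fraction c of the hidden prevalent comparators and none of the recipients, with f defined before that removal. Then RR observed = [RR true (1 - f) + f] / [(1 - f) + f(1 - c)].

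With f = 0.3:
- True RR 1, c = 0.5: 1/0.85 = 1.18
- True RR 1, c = 0.75: 1/0.775 = 1.29
- True RR 2, c = 0.5: 1.70/0.85 = 2.00
- True RR 2, c = 0.75: 1.70/0.775 = 2.19

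The bias can therefore be downward, nil or upward.

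**The case against.** **Direction.** A reader might infer that the MS rate ratio is simply diluted. The documents do not support that. Dilution needs an equal leak, and Day 0 screening gives a reason why it may be unequal. How unequal depends on how many comparators enter on an office visit rather than on another vaccine, which is not known. This objection stands.

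**Route.** A reader might also infer that G35 codes on infusion or imaging claims are ignored in the clean period. Section 17.3 read alone suggests so, but the Table 2 footnote may let those claims count, which would largely close that route. What remains is the person whose baseline-year evidence of MS is pharmacy fills.

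**Size.** Section 9.9 expects most people with a chronic condition to have contact with care at least yearly, and treated patients may be the likeliest to do so. That is fair, and the leak may be small. However, a refill is a contact without a diagnosis, and where Section 9.9 admits that people without a visit may be missed, it does so for covariates only. Much larger shares can be generated: prevalence 200 to 400 per 100,000, 50% to 60% treated, a 1% to 5% leak and incidence 5 to 8 per 100,000 give 11% to 71% false cases. Every one of those inputs is assumed, and the calculation recodes every leaked patient, so that range should carry no weight.

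**Relapse.** Section 7 cites reports of relapse or progression of MS, so counting existing disease might seem intended. Section 9.1.1 asks for incident outcomes, and one G35 code does not separate a relapse from a routine visit.

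**Reach of the fix.** A drug filter leaves untreated prevalent MS in place. For illustration, assume prevalence 300 per 100,000, 60% treated, a 2% leak among the treated, incidence 5 per 100,000 and true RR 2. If the untreated also leak at 2%, false cases are 3.6 + 2.4 = 6.0 and the RR reads 16/11 = 1.45. With the treated removed it reads 12.4/7.4 = 1.68. If the untreated leak at 5%, the RR goes from 19.6/14.6 = 1.34 to 16/11 = 1.45. This limit stands.

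**Conclusion.** The gap holds on the text: the MS clean period consults only the G35 outcome, so a treated patient with no qualifying visit in the baseline year is later counted as new, against the stated aim of incident outcomes. The listing of these drugs as covariates is not itself an error. The weakness lies in the outcome-specific exclusion.

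Direction and size are not established. With an equal leak and an assumed 10% to 50% of comparator cases prevalent, a true RR of 2 reads 1.90 to 1.50. With an unequal leak through Day 0, a true RR of 1 can read 1.18 to 1.29 (assumed f = 0.3, c = 0.5 to 0.75). Nor do the documents say which listed drugs are specific to MS; the protocol groups them by class, without indications.

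The point is worth acting on because the same filter applies to both groups whichever way the bias runs, and because it uses data already extracted.

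**What to change.** 1. In Section 9.2.1.1 criterion 5 and the last paragraph of Section 9.2.2.2, add for the MS outcome: also exclude anyone who, in Days -365 to 0, has (a) a pharmacy or medical claim for a prespecified, named subset of MS-specific agents already in Section 17.4.2.1, or (b) G35 on any claim in any setting.
2. Candidate subset, with the sponsor to confirm the indications: interferon beta, peginterferon beta-1a, glatiramer, ocrelizumab, ublituximab, fingolimod, siponimod, ponesimod, teriflunomide, and dimethyl and diroximel fumarate, with HCPCS J1595, J1826, J1830, J2329, J2350, Q3027 and Q3028. Leave out agents that the sponsor finds have other uses.
3. Report the MS rate ratio with and without this rule. The difference shows how much the leak mattered.
4. Reconcile the outpatient definition in Section 17.3 with the Table 2 footnote.

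The cost is one added rule and one filter, applied where Section 9.7.2.1 already makes outcome-specific exclusions. Because the matched comparators of excluded individuals also drop out there, some matched sets and some MS cases are lost; the loss should be small. Prevalent MS with neither a listed drug nor a G35 claim in the year remains, and Section 9.9 should say so.
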